### **Prior/Concomitant Therapy**

21. Has received a live-virus vaccine within 28 days of planned treatment start. Seasonal flu vaccines that do not contain live virus are permitted.
22. Has received prior therapy with compounds targeting PD-1, PD-L1, PD-L2, an MEK inhibitor (eg, cobimetinib, trametinib), or an ERK inhibitor (eg, MK-8353, GCD-0994, ulixertinib).

### **Prior/Concurrent Clinical Study Experience**

23. Is currently participating and receiving study treatment in a study of an investigational agent or has participated and received study treatment in a study of an investigational agent or has used an investigational device within 28 days of administration of selumetinib.

Note: Participants who have entered the follow-up phase of an investigational study may participate as long as it has been 4 weeks since the last dose of the previous investigational agent.

### **Pregnancy Exclusion**

24. A WOCBP who has a positive urine pregnancy test within 24 hours before the first dose of study treatment (see Appendix 5). If the urine test cannot be confirmed as negative, a serum pregnancy test is required. In such cases, the participant must be excluded from participation if the serum pregnancy result is positive.

### **5.3 Special Consideration for Participants of Asian Ethnicity**

Plasma exposure of selumetinib ( $C_{max}$  and AUC) is higher, at a population level, in subjects of Asian ethnicity by approximately 1.5- to 2-fold compared with Western subjects. However, the PKs of selumetinib show considerable variation and there is overlap in the range of exposure experienced by Asian and Western subjects (some individual Asian subjects have similar plasma levels to those in Western subjects). The higher average plasma exposure was not associated with a change in the tolerability profile of single dose selumetinib.

Patients of Asian ethnicity are not excluded from studies evaluating selumetinib. However, when considering enrolling an individual of Asian ethnicity to a selumetinib clinical study, investigators should make a clinical judgment as to whether the potential risk of experiencing higher selumetinib plasma levels outweighs the potential benefit of treatment with selumetinib. The Patient Information and Consent form for studies of selumetinib includes information on the possibility of higher selumetinib plasma levels and occurrence of AEs in Asian subjects than in subjects who are not of Asian origin. Investigators should be aware of the potentially higher risk of adverse events when monitoring patients of Asian ethnicity receiving treatment in clinical studies of Selumetinib.

Additional details are available in the selumetinib IB.

#### **5.4 Lifestyle Considerations**

##### **5.4.1 Meals and Dietary Restrictions**

Selumetinib should be taken on an empty stomach (no food or drink other than water for approximately 2 hours prior to dosing and approximately 1 hour after dosing).

##### **5.4.2 Caffeine, Alcohol, and Tobacco Restrictions**

There are no study-specific restrictions.

##### **5.4.3 Activity Restrictions**

There are no study-specific restrictions.

#### **5.5 Screen Failures**

Screen failures are defined as participants who consent to participate in the clinical study, but are not subsequently entered in the study. A minimal set of screen failure information is required to ensure transparent reporting of screen failure participants to meet the Consolidated Standards of Reporting Trials (CONSORT) publishing requirements and to respond to queries from regulatory authorities. Minimal information includes demography, screen failure details, eligibility criteria, and any AEs or SAEs meeting reporting requirements as outlined in the data entry guidelines.

#### **5.6 Participant Replacement Strategy**

In order to adequately evaluate the safety of the doses administered in this study, all participants enrolled must meet the criteria for evaluability for Cycle 1. Participants are considered nonevaluable and will be replaced if:

- They are allocated but not treated.
- They discontinue from the trial prior to completing all the safety evaluations for reasons other than treatment-related AEs.

- They receive less than 75% of the total selumetinib or pembrolizumab study treatment in Cycle 1 and did not experience a DLT.

Participants who are not evaluable will be replaced unless accrual to the cohort has stopped. Nonevaluable participants will not be counted toward the total number of participants in the cohort for DLT evaluation.

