## 6.5.2 Prohibited Concomitant Medications

Participants are prohibited from receiving the following therapies during the Screening and Treatment Phases of this study:

- Antineoplastic systemic chemotherapy or biological therapy
- Immunotherapy not specified in this protocol
- Chemotherapy not specified in this protocol
- Investigational agents other than selumetinib (MK 5618) and pembrolizumab (MK-3475).
- For agents that may affect the metabolism of selumetinib (eg, strong inhibitors and inducers of CYP2C19 or CYP3A4), caution should be taken. However, changes in exposure of selumetinib with strong inhibitors/inducers would be moderate based on clinical evidence (1.5-fold).
- Participants should not take any supplemental vitamin E. High doses of vitamin E have been reported to cause bleeding and interrupt blood coagulation processes.

Note: Selumetinib capsules contain vitamin E in the form of D-a-tocopheryl polyethylene glycol 1000 succinate (TPGS), a water-soluble form of vitamin E, which acts as a formulation excipient.

- Radiation therapy

Note: Radiation therapy to a symptomatic solitary lesion or to the brain may be allowed at the investigator's discretion after the DLT observation period.

- Live vaccines within 28 days prior to the first dose of study intervention and while participating in the study. Examples of live vaccines include, but are not limited to the following: measles, mumps, rubella, varicella/zoster, yellow fever, rabies, Bacillus Calmette–Guérin, and typhoid vaccine. Seasonal influenza vaccines for injection are generally killed virus vaccines and are allowed; however, intranasal influenza vaccines (eg, FluMist®) are live attenuated vaccines and are not allowed.
- Systemic glucocorticoids for any purpose other than to modulate symptoms from an AE of suspected immunologic etiology. The use of physiologic doses of corticosteroids may be approved after consultation with the Sponsor.

Participants who, in the assessment by the investigator, require the use of any of the aforementioned treatments for clinical management should be removed from the study. Participants may receive other medications that the investigator deems to be medically necessary.

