6. An elevated AST or ALT lab value that is  $\geq3X$  the upper limit of normal and an elevated total bilirubin lab value that is  $\geq2X$  the upper limit of normal and, at the same time, an alkaline phosphatase lab value that is  $<2X$  the upper limit of normal, as determined by way of protocol-specified laboratory testing or unscheduled laboratory testing.
7. Any prolonged delay ( $>2$  weeks) in initiating Cycle 2 study treatment due to a treatment-related toxicity.
8. Any treatment-related toxicity that causes the participant to discontinue treatment during Cycle 1.
9. Missing  $>25\%$  of selumetinib doses as a result of drug-related AE(s) during the first treatment cycle.

10. Grade 5 toxicity

11. Cardiac disorders

- Absolute decrease in LVEF  $>10\%$  compared with baseline and the LVEF is below the institution's lower limit of normal
- Left ventricular systolic dysfunction Grade  $\geq3$
- Other cardiac disorders Grade  $\geq3$

12. Vascular disorders

- Hypertension CTCAE Grade  $\geq3$  requiring more than 1 drug or more intensive therapy
- Grade 4 hypertension

13. Eye disorders

- Retinopathy or retinal detachment Grade  $\geq3$ , confirmed by ophthalmic examination

- Retinal vein disorder including RVO, confirmed by ophthalmic examination
- Visual disturbances without ocular (retinal) changes
- Blurred vision, flashing lights, floaters: Grade  $\geq 3$
- Other (not listed above)
- Grade  $\geq 3$  for  $>21$  consecutive days
- Grade 4 confirmed by ophthalmic examination

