# **7 DISCONTINUATION OF STUDY INTERVENTION AND PARTICIPANT WITHDRAWAL**

## **7.1 Discontinuation of Study Intervention**

Discontinuation of study intervention does not represent withdrawal from the study.

As certain data on clinical events beyond study intervention discontinuation may be important to the study, they must be collected through the participant's last scheduled follow-up, even if the participant has discontinued study intervention. Therefore, all participants who discontinue study intervention prior to completion of the protocol-specified treatment period will still continue to participate in the study as specified in Section 1.3 and Section 8.10.3.

Participants may discontinue study intervention at any time for any reason or be discontinued from the study intervention at the discretion of the investigator should any untoward effect occur. In addition, a participant may be discontinued from study intervention by the investigator or the Sponsor if study intervention is inappropriate, the study plan is violated, or for administrative and/or other safety reasons. Specific details regarding procedures to be performed at study intervention discontinuation are provided in Section 8.1.9 and Section 8.10.3.

A participant must be discontinued from study intervention but continue to be monitored in the study for any of the following reasons:

- The participant or participant's legally acceptable representative requests to discontinue study intervention.
- The participant interrupts study intervention administration for more than 21 consecutive days during the 3-week cycle.
- The participant has a medical condition or personal circumstance which, in the opinion of the investigator and/or Sponsor, placed the participant at unnecessary risk from continued administration of study intervention.
- The participant has a confirmed positive serum pregnancy test.
- Confirmed radiographic disease progression outlined in Section 8.2 (exception if the Sponsor approves treatment continuation).
- Unacceptable adverse experiences as described in Section 8.3.
- Progression or recurrence of any malignancy, or any occurrence of another malignancy that requires active treatment.
- Intercurrent illness other than another malignancy as noted above that prevents further administration of treatment.
- Investigator's decision to discontinue the participant.
- Recurrent Grade 2 pneumonitis.

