## 7.2 Participant Withdrawal From the Study

A participant must be withdrawn from the study if the participant or participant's legally acceptable representative withdraws consent from the study.

If a participant withdraws from the study, they will no longer receive study intervention or be followed at scheduled protocol visits.

Specific details regarding procedures to be performed at the time of withdrawal from the study, as well as specific details regarding withdrawal from future biomedical research, are outlined in Section 8.1.9. The procedures to be performed should a participant repeatedly fail to return for scheduled visits and/or if the study site is unable to contact the participant are outlined in Section 7.3.

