## 9.5 Analysis Populations

### 9.5.1 Safety Analysis Populations

The All-Participants-as-Treated (APaT) population will be used for the analysis of safety data in this study. The APaT population consists of all participants who received at least 1 dose of study treatment.

The DLT evaluable population includes APaT participants that meet the criteria for DLT evaluability (eg, finished Cycle 1 without a DLT or experienced a DLT in Cycle 1). See Section 6.6.2.2 for details.

At least 1 laboratory or vital sign measurement obtained subsequent to at least 1 dose of study treatment is required for inclusion in the analysis of each specific parameter. To assess change from baseline, a baseline measurement is also required.

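### The second replacement rule in Section 5.6 has no DLT exception, so read literally it drops an observed Cycle 1 DLT that Section 9.5.1 treats as evaluable

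*Combined protocol and SAP*

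**What the plan says.** Section 5.6 gives three separate grounds on which a participant is nonevaluable for Cycle 1 and is replaced. The first is allocation without treatment. The second is: "They discontinue from the trial prior to completing all the safety evaluations for reasons other than treatment-related AEs". The third is: "They receive less than 75% of the total selumetinib or pembrolizumab study treatment in Cycle 1 and did not experience a DLT". The section then states the consequence: "Nonevaluable participants will not be counted toward the total number of participants in the cohort for DLT evaluation". Replacement is waived only if accrual to the cohort has stopped.

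Section 9.5.1 describes the DLT-evaluable population by example: "eg, finished Cycle 1 without a DLT or experienced a DLT in Cycle 1). See Section 6.6.2.2 for details". Section 6.6.2.2, to which it points, defines DLTs and the 21-day window but contains no evaluability criteria. The column header of Table 1 (Section 4.3.1.4) makes the number evaluable for DLT the denominator of the dose decision.

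**The concern.** The exception in the second bullet concerns why the participant left, not whether a DLT had already been seen. The third bullet protects observed DLTs explicitly. A participant who has a Cycle 1 DLT and then leaves the trial for an unrelated reason is nonevaluable under Section 5.6 and evaluable under Section 9.5.1, and the cross-reference that should settle the matter does not.

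DLT incidence is a primary endpoint, and its count drives every escalation decision. If the second bullet is followed as written, an observed DLT leaves that count. With a DLT-free replacement the action stays the same or becomes less cautious, and a dose marked unacceptably toxic can lose that mark. The event would still appear in the AE and DLT listings, so what is at stake is the dose decision and the estimated DLT rate, not whether the event is reported.

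**Working it through.** **1. Which participants are affected**

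- Leaving because of the DLT: a DLT must be assessed as drug-related, so this is a treatment-related AE and the second bullet keeps the participant.
- Stopping treatment in Cycle 1 for related toxicity: this is itself DLT criterion 8 ("Any treatment-related toxicity that causes the participant to discontinue treatment during Cycle 1").
- Stopping treatment only: Section 7.1 says "Discontinuation of study intervention does not represent withdrawal from the study".
- What remains is a Cycle 1 DLT followed by departure from the study for another reason. The clean route is Section 7.2, where the participant or "legally acceptable representative withdraws consent from the study". A second route is Section 6.5.2, under which participants who "require the use of any of the aforementioned treatments for clinical management should be removed from the study".

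**2. Reproducing Table 1**

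Inputs from the Table 1 footnotes: target 0.30, prior Beta(1,1), both epsilons 0.03. With x DLTs in n participants the posterior is Beta(1+x, 1+n−x) with distribution function F. The action is the interval with the largest unit probability mass:

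- E: F(0.27)/0.27
- S: [F(0.33) − F(0.27)]/0.06
- D: [1 − F(0.33)]/0.67
- DU if 1 − F(0.30) > 0.95. The 0.95 cutoff is an assumption, since the documents do not state it.

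Examples:

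- 1/3: F(0.27) = 0.2959 and F(0.33) = 0.4015, giving masses 1.10, 1.76 and 0.89, so S.
- 0/3: F(0.27) = 0.7160 and F(0.33) = 0.7985, giving 2.65, 1.37 and 0.30, so E.

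All 78 cells in rows 0 to 6 match the printed table. Rows 7 and 8 are broken in the text available and were not used.

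**3. One DLT discarded, DLT-free replacement: x/n becomes (x−1)/n**

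Over rows 1 to 6 and n = 3 to 14 there are 66 filled cells. The action changes in 27, always to a less cautious one: S to E in 12, D to S in 6, DU to D in 5, DU to S in 4. So 5 + 4 = 9 of the 16 DU cells lose the mark. For n = 3 to 6, 10 of 18 cells change:

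| n | Changes |
|---|---|
| 3 | 1/3 S to E; 2/3 D to S; 3/3 DU to D |
| 4 | 1/4 S to E; 3/4 DU to S |
| 5 | 1/5 S to E; 3/5 D to S; 4/5 DU to D |
| 6 | 2/6 S to E; 4/6 DU to S |

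**4. One DLT discarded, no replacement: x/n becomes (x−1)/(n−1)**

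For n = 4 to 14, 19 of 63 cells change, all to a less cautious action; for example, 1/4 S becomes 0/3 E and 4/6 DU becomes 3/5 D.

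**5. Probability of a changed action, given one discarded DLT**

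Let k ~ Binomial(n−1, p) be the DLTs among the others, and let the replacement have a DLT with probability p. Then P(less cautious) = (1−p) × the sum of P(k) over those k where the actions at (k+1)/n and k/n differ.

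At p = 0.30:

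- n = 3: all k count, 0.7 × 1 = 0.700
- n = 4: k = 0, 2, 0.7 × (0.3430 + 0.1890) = 0.372
- n = 5: k = 0, 2, 3, 0.7 × (0.2401 + 0.2646 + 0.0756) = 0.406
- n = 6: k = 1, 3, 0.7 × (0.3601 + 0.1323) = 0.345

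For n = 3 to 6, p = 0.20 gives 0.800, 0.486, 0.471, 0.369 and p = 0.40 gives 0.600, 0.302, 0.377, 0.294.

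**6. Unconditional size, under an assumed leaving rate**

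The documents give no rate. The share of participants with a DLT who leave this way is assumed, at p = 0.30 with random replacement outcomes:

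| Assumed share | n = 3 | n = 4 | n = 5 | n = 6 |
|---|---|---|---|---|
| 2% | 0.0125 | 0.0090 | 0.0121 | 0.0124 |
| 5% | 0.0312 | 0.0225 | 0.0302 | 0.0310 |
| 10% | 0.0617 | 0.0451 | 0.0599 | 0.0618 |

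**7. Long-run direction**

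Take p = 0.30 and a 10% leaving rate. If leaving is unrelated to DLT status, the literal rule leaves the expected rate at 0.30, while keeping only the leavers with a DLT gives 0.30/(0.30 + 0.70 × 0.90) = 0.323. If only participants with a DLT leave, the literal rule gives 0.27/(0.27 + 0.70) = 0.278. The direction depends on something the documents do not show.

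**8. Final estimate**

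With the Beta(1,1) prior of Section 9.6.2, 4/14 (28.6%, 80% credible interval 17.2% to 46.4%) would become 3/14 (21.4%, 12.2% to 39.3%).

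**The case against.** The strongest reply is that the intended answer is already in the plan, in the third bullet and in Section 9.5.1, and that no sensible team would ignore an observed DLT. The closing sentence of Section 5.6 can also be read as concerning only the denominator. The first part is fair as to intent: this looks like a drafting omission. It does not make the text consistent, because the authors thought the exception needed writing in one bullet and left it out of the one before. The denominator-only reading does not fit Table 1, whose decisions rest on participants evaluable for DLT; a DLT in the numerator with no matching participant in the denominator is not a defined cell.

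The event is also rare. It needs a DLT, then departure from the study rather than from treatment, for an unrelated reason, within what is left of 21 days. That stands. The prohibited-therapy route is weaker than withdrawal of consent: Section 8.1.5.2 moves participants who start another anticancer therapy into survival follow-up, so they stay in the study. That closes the route for anticancer therapy only. Section 4.1 adds uncertainty by saying that participants who stop for progression and other reasons are discontinued from the study, which sits badly with Section 7.1.

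Finally, the cell counts are not weighted by probability, and 5 of the 27 changes are DU to D, where de-escalation follows either way. This also stands. Merging D and DU lowers the conditional probability for n = 3 from 0.700 to 0.637 and for n = 5 from 0.406 to 0.353; n = 4 and n = 6 do not change.

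**Conclusion.** The concern holds and should be fixed. Sections 5.6 and 9.5.1 disagree on whether a participant with an observed Cycle 1 DLT counts, and Section 5.6 as written leaves that participant out. The contradiction is certain. Its consequence is conditional: decisive in small cohorts when the case arises (probability about 0.34 to 0.70 of a less cautious action at a true rate of 30%), but affecting only about 1% to 6% of cohorts of 3 to 6 if 2% to 10% of participants with a DLT left this way. Those leaving rates are assumptions. The Table 1 results rest on the printed cells in rows 0 to 6; the 0.95 cutoff was needed only to confirm that those cells follow the mTPI rule.

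**What to change.** Add to the second bullet of Section 5.6 the same DLT exception that the third bullet carries, so that anyone with an observed Cycle 1 DLT remains evaluable whatever the later reason for leaving. This agrees with Section 9.5.1 and sets no dose or clinical rule.

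Three editorial points can go in the same amendment:

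- Section 9.5.1 should refer to Section 5.6, not 6.6.2.2, for evaluability.
- Section 4.3.1.4 should describe the decision inputs and the Table 1 columns as participants evaluable for DLT, instead of enrolled or treated.
- Sections 9.1 and 9.6.2 should name the DLT-evaluable population for the isotonic estimates and the DLT rate at the RP2D.

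The cost is one clause plus wording. Sample size and Table 1 do not change.

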## 6 STUDY INTERVENTION

Study intervention is defined as any investigational intervention(s), marketed product(s), placebo, or medical device(s) intended to be administered to a study participant according to the study protocol.

Study intervention supplies provided by the Sponsor will be packaged to support enrollment. Study intervention supplies will be affixed with a clinical label in accordance with regulatory requirements.

### 6.1 Study Intervention(s) Administered

The study intervention(s) to be used in this study are outlined in [Table 3](#).

Table 3 Study Interventions

Arm Name	Arm Type	Intervention Name	Type	Dose Formulation	Unit Dose Strength(s)	Dosage Level(s)	Route of Administration	Regimen / Treatment Period / Vaccination Regimen	Use	IMP/ NIMP	Sourcing
Selumetinib + Pembrolizumab	Experimental	Selumetinib (MK-5618)	Drug	Capsule	25 mg	50 mg 75 mg 100 mg 125 mg 150 mg 200 mg Above 200 mg (up to 300 mg)	Oral	BID: 2 weeks on followed by 1 week off	Experimental	IMP	Provided centrally by Sponsor
Selumetinib + Pembrolizumab	Experimental	Pembrolizumab (MK-3475)	Drug	Vial	200 mg	200 mg	IV Infusion	Q3W	Experimental	IMP	Provided centrally by Sponsor

Abbreviations: BID = twice daily; IV = intravenous; Q3W = every 3 weeks  
 Definition Investigational Medicinal Product (IMP) and Non-Investigational Medicinal Product (NIMP) is based on guidance issued by the European Commission. Regional and/or Country differences of the definition of IMP/NIMP may exist. In these circumstances, local legislation is followed.

All supplies indicated in [Table 3](#) will be provided per the "Sourcing" column depending upon local country operational requirements. If local sourcing, every attempt should be made to source these supplies from a single lot/batch number where possible (eg, not applicable in the case where multiple lots or batches may be required due to the length of the study, etc.).

Refer to Section 8.1.8 for details regarding administration of the study intervention.

## **6.2 Preparation/Handling/Storage/Accountability**

### **6.2.1 Dose Preparation**

There are no specific calculations or evaluations required to be performed in order to administer the proper dose to each participant. The rationale for selection of doses to be used in this study is provided in Section 4.3.

### **6.2.2 Handling, Storage, and Accountability**

The investigator or designee must confirm appropriate temperature conditions have been maintained during transit for all study intervention received, and any discrepancies are reported and resolved before use of the study intervention.

Only participants enrolled in the study may receive study intervention, and only authorized site staff may supply or administer study intervention. All study interventions must be stored in a secure, environmentally controlled, and monitored (manual or automated) area in accordance with the labeled storage conditions with access limited to the investigator and authorized site staff.

The investigator, institution, or the head of the medical institution (where applicable) is responsible for study intervention accountability, reconciliation, and record maintenance (ie, receipt, reconciliation, and final disposition records).

For all study sites, the local country Sponsor personnel or designee will provide appropriate documentation that must be completed for drug accountability and return, or local discard and destruction if appropriate. Where local discard and destruction is appropriate, the investigator is responsible for ensuring that a local discard/destruction procedure is documented.

The study site is responsible for recording the lot number, manufacturer, and expiry date for any locally purchased product (if applicable) as per local guidelines unless otherwise instructed by the Sponsor.

The investigator shall take responsibility for and shall take all steps to maintain appropriate records and ensure appropriate supply, storage, handling, distribution, and usage of study interventions in accordance with the protocol and any applicable laws and regulations.

